#### Post-infusion medication

For the prevention of delayed IRRs, oral corticosteroid (20 mg methylprednisolone or equivalent dose of a corticosteroid in accordance with local standards) should be administered on each of the two days following all infusions (beginning the day after the infusion).

Additionally, for patients with a history of obstructive pulmonary disorder, the use of post-infusion medications including short and long acting bronchodilators, and inhaled corticosteroids should be

considered. Following the first four infusions, if the patient experiences no major IRRs, these inhaled post-infusion medications may be discontinued at the discretion of the physician.

**Prophylaxis for herpes zoster virus reactivation**

Anti-viral prophylaxis should be considered for the prevention of herpes zoster virus reactivation.

**Infection Prophylaxis:** Prophylactic use of antibiotics is highly recommended due to the susceptibility of multiple myeloma patients to infections. Prophylactic administration of levofloxacin (500 mg P.O. daily; dose adjusted for renal function) **during the first 3 cycles of treatment** is recommended as it has shown to significantly reduce febrile episodes and deaths without increasing healthcare associated infections or carriage of key nosocomial pathogens.

**HBV prophylaxis:** Primary antiviral prophylaxis for HBV reactivation is permitted as per local standard of care. Please refer to Section 7.1.4 for more details about the management of HBV reactivation

Source: Drayson, Mark T et al "Tackling Early Morbidity and Mortality in Myeloma (TEAMM): Assessing the Benefit of Antibiotic Prophylaxis and Its Effect on Healthcare Associated Infections in 977 Patients." *Blood* 130 Suppl 1 (2017):903

## Appendix 3a – The International Staging System (ISS) for Multiple Myeloma

Stage	Criteria	Median Survival (Months)
Stage 1	Serum $\beta$ 2-microglobulin $< 3.5$ mg/L Serum albumin $\geq 3.5$ g/dL	62
Stage 2	Not stage I or III (There are two categories for stage II)  serum $\beta$ 2-microglobulin $< 3.5$ mg/L but serum albumin $< 3.5$ g/dL OR  $\beta$ 2-microglobulin 3.5 to $< 5.5$ mg/L irrespective of the serum albumin level	44
Stage 3	Serum $\beta$ 2-microglobulin $\geq 5.5$ mg/L	29

## Appendix 3b – The Revised International Staging System (ISS) for Multiple Myeloma

Stage	Criteria	Median Survival (Months)
Stage 1	ISS stage I and standard-risk CA by iFISH and normal LDH	Not reached
Stage 2	Not R-ISS stage I or III	83
Stage 3	ISS stage III and either high-risk CA by iFISH or high LDH	43

Abbreviations: ISS: International Staging System, CA: chromosomal abnormalities, LDH: lactate dehydrogenase; R-ISS, revised International Staging System.

Chromosomal abnormalities detected by iFISH:

High risk: del(17p), and/or translocation t(4;14), and/or translocation t(14;16)

Standard risk: No high-risk CA

LDH:

Normal: Serum LDH  $<$  the upper limit of normal

High: Serum LDH  $>$  the upper limit of normal

## Appendix 4 – Modified International Myeloma Working Group (IMWG) Uniform Response Criteria for Multiple Myeloma

Response	IMWG criteria
Stringent complete response (sCR)	CR as defined below plus normal FLC ratio and absence of clonal cells in bone marrow  by immunohistochemistry or immunofluorescence. 
Complete response (CR)	Negative immunofixation on serum and urine and disappearance of any soft tissue plasmacytomas and < 5% plasma cells in bone marrow. 
Very good partial response (VGPR)	Serum and urine M-protein detectable by immunofixation but not on electrophoresis or $\geq 90\%$ reduction in serum M-protein plus urine M-protein level < 100 mg/24 h
Partial response (PR)	$\geq 50\%$ reduction of serum M-protein and reduction in 24 hours urinary M-protein by $\geq 90\%$ or to < 200 mg/24 h. If serum and urine M-protein are unmeasurable,  a $\geq 50\%$ decrease in the difference between involved and uninvolved FLC levels is required in place of the M-protein criteria. If serum and urine M-protein are not measurable, and serum free light assay is also not measurable, $\geq 50\%$ reduction in plasma cells is required in place of M-protein, provided baseline bone marrow plasma cell percentage was $\geq 30\%$ . In addition to the above listed criteria, if present at baseline, a $\geq 50\%$ reduction in the size of soft tissue plasmacytomas is also required.
Minor (Minimal) Response (MR)	25-49% reduction of serum M-protein and reduction in 24-hour urine M-protein by 50-89%, which still exceeds 200 mg per 24 hours. In addition, if present at baseline, 25-49% reduction in the size of soft tissue plasmacytomas is also required. No increase in the size or number of lytic bone lesions (development of compression fracture does not exclude response).
No change/Stable disease (SD)	Not meeting criteria for CR, VGPR, PR, or progressive disease.
Progressive disease (PD) 	Any of the following: 
 
• Increase of <math>\geq 25\%</math> from lowest response value in any one or more of the following:                             
 
◦ Serum M-component and/or (the absolute increase must be <math>\geq 0.5</math> g/dL)
 
◦ Urine M-component and/or (the absolute increase must be <math>\geq 200</math> mg/24 h)
 
◦ Only in patients without measurable serum and urine M-protein levels; the difference between involved and uninvolved FLC levels. The absolute increase must be <math>> 10</math> mg/dL
 
◦ Bone marrow plasma cell percentage; the absolute percentage must be <math>\geq 10\%</math>
 
 
 
• Definite development of new bone lesions or soft tissue plasmacytomas or definite increase in the size of existing bone lesions or soft tissue plasmacytomas (<math>\geq 50\%</math> increase from nadir in SPD of <math>> 1</math> lesion, or <math>\geq 50\%</math> increase in the longest diameter of a previous lesion <math>> 1</math> cm in the short axis).
 
• Development of hypercalcemia (corrected serum calcium <math>> 11.5</math> mg/dL or 2.87 mmol/L) that can be attributed solely to the plasma cell proliferative disorder
 

Relapse	
Clinical relapse requires one or more of:
 
Direct indicators of increasing disease and/or end organ dysfunction (CRAB features). It is not used in calculation of time to progression or progression-free survival but is listed here as something that can be reported optionally or for use in clinical practice
 

• Development of new soft tissue plasmacytomas or bone lesions

• Definite increase in the size of existing plasmacytomas or bone lesions. A definite increase is defined as a 50% (and at least 1 cm) increase as measured serially by the sum of the products of the cross-diameters of the measurable lesion

• Hypercalcemia (<math>> 11.5 \text{ mg/dL}</math>) [<math>2.87 \text{ mmol/L}</math>]

• Decrease in hemoglobin of <math>\geq 2 \text{ g/dL}</math> [<math>1.24 \text{ mmol/L}</math>]

• Rise in serum creatinine by 2 mg/dL or more [<math>177 \mu\text{mol/L}</math> or more]

Relapse from CR  (To be used only if the end point studied is DFS) 	Any one or more of the following: 

• Reappearance of serum or urine M-protein by immunofixation or electrophoresis

• Development of <math>\geq 5\%</math> plasma cells in the bone marrow

• Appearance of any other sign of progression (i.e., new plasmacytoma, lytic bone lesion, or hypercalcemia)

Note: A clarification to IMWG criteria for coding CR and VGPR in patients in whom the only measurable disease is by serum FLC levels: CR in such patients is defined as a normal FLC ratio of 0.26–1.65 in addition to CR criteria listed above. VGPR in such patients is defined as a  $>90\%$  decrease in the difference between involved and uninvolved free light chain (FLC) levels.

 Confirmation with repeat bone marrow biopsy not needed.

 Presence/absence of clonal cells is based upon the kappa/lambda ratio. An abnormal kappa/lambda ratio by immunohistochemistry and/or immunofluorescence requires a minimum of 100 plasma cells for analysis. An abnormal ratio reflecting presence of an abnormal clone is kappa/lambda of  $> 4:1$  or  $< 1:2$ .

 All relapse categories require two consecutive assessments made at any time before classification as relapse or disease progression and/or the institution of any new therapy. In the IMWG criteria, CR patients must also meet the criteria for progressive disease shown here to be classified as progressive disease for the purposes of calculating time to progression and progression-free survival. The definitions of relapse, clinical relapse and relapse from CR are not to be used in calculation of time to progression or progression-free survival.

 For progressive disease, serum M-component increases of  $\geq 1 \text{ gm/dL}$  are sufficient to define relapse if starting M-component is  $\geq 5 \text{ g/dL}$ .

 Relapse from CR has the 5% cut-off versus 10% for other categories of relapse.

 For purposes of calculating time to progression and progression-free survival, CR patients should also be evaluated using criteria listed above for progressive disease.

 SPD = sum of the products of the maximal perpendicular diameters of measured lesions

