APPENDIX 1) as their best overall response.

The response rate, along with its exact two-sided 95% CI, will be computed.

Renal Response Rate (RRR)

Rrr is defined as the proportion enrolled subjects who achieve a best response of renal partial renal response (PRRenal) or better using the criteria of the International Myeloma Working Group (IMWG) (APPENDIX 2).

Duration of Response (DoR)

DoR will be restricted to the subjects that achieve a best objective response of PR or better. It is measured from the time, in months, that the criteria for objective response are first met until the date of a progression event (according to the primary definition of PFS). A subject with objective response who does not have a progression event will be censored at the same time they were censored under the primary definition of PFS.

The DoR function will be estimated using the Kaplan-Meier product-limit method. Median and two-sided confidence intervals for median duration of response will be computed and Kaplan-Meier plots of DoR will be presented.

Time to Next Therapy (TNT)

TNT will be defined as the time, in months, from Cycle 1 Day 1 to the date to next anti-neoplastic therapy or death from any cause, whichever comes first. For subjects who neither start a new anti-neoplastic therapy nor die, survival time will be censored at the date of their last available follow-up assessment.

Time to next therapy will be calculated using a log-rank test procedure. The TNT function will be estimated using the Kaplan-Meier product-limit method. Median and two-sided confidence intervals for median TNT will be computed. Kaplan-Meier plots of TNT will be presented.

Overall Survival (OS)

Overall survival is defined as the time, in months, from the first dose of therapy to the date of death from any cause. If a patient is not known to have died, survival time will be censored at the date of last contact (“last known date alive”).

Overall survival will be estimated using the Kaplan-Meier product-limit method. Median and corresponding two-sided 95% confidence intervals will be computed. Kaplan-Meier plots of OS will be presented.

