6.7 References

1. Rajan, A. M., and S. V. Rajkumar. "Interpretation of cytogenetic results in multiple myeloma for clinical practice." *Blood cancer journal* 5.10 (2015): e365.

Health Data Specialists	
DARE (EAE-2017/MM02)- Statistical Analysis Plan	Version: 1.0 EN
Author: GC, Reviewer: MS, Quality Assurance: GK	Date: 02-02-2018

APPENDIX 1

Table 6. Modified International Myeloma Working Group (IMWG) Uniform Response Criteria for Multiple Myeloma

Response	IMWG criteria
Stringent complete response (sCR)	CR as defined below plus normal FLC ratio and absence of clonal cells in bone marrow ¹ by immunohistochemistry or immunofluorescence. ²
Complete response (CR)	Negative immunofixation on serum and urine and disappearance of any soft tissue plasmacytomas and < 5% plasma cells in bone marrow. ¹
Very good partial response (VGPR)	Serum and urine M-protein detectable by immunofixation but not on electrophoresis or $\geq 90\%$ reduction in serum M-protein plus urine M-protein level $< 100 \text{ mg/24 h}$
Partial response (PR)	$\geq 50\%$ reduction of serum M-protein and reduction in 24 hours urinary M-protein by $\geq 90\%$ or to $< 200 \text{ mg/24 h}$. If serum and urine M-protein are unmeasurable, ³ a $\geq 50\%$ decrease in the difference between involved and uninvolved FLC levels is required in place of the M-protein criteria. If serum and urine M-protein are not measurable, and serum free light assay is also not measurable, $\geq 50\%$ reduction in plasma cells is required in place of M-protein, provided baseline bone marrow plasma cell percentage was $\geq 30\%$. In addition to the above listed criteria, if present at baseline, a $\geq 50\%$ reduction in the size of soft tissue plasmacytomas is also required.
Minor (Minimal) Response (MR)	25-49% reduction of serum M-protein and reduction in 24-hour urine M-protein by 50-89%, which still exceeds 200 mg per 24 hours. In addition, if present at baseline, 25-49% reduction in the size of soft tissue plasmacytomas is also required. No increase in the size or number of lytic bone lesions (development of compression fracture does not exclude response).
No change/Stable disease (SD)	Not meeting criteria for CR, VGPR, PR, or progressive disease.

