Progressive disease (PD) ³	Any of the following: 
 • Increase of $\geq 25\%$ from lowest response value in any one or more of the following: 
 ◦ Serum M-component and/or (the absolute increase must be $\geq 0.5 \text{ g/dL}$)⁴ ◦ Urine M-component and/or (the absolute increase must be $\geq 200 \text{ mg/24 h}$) ◦ Only in patients without measurable serum and urine M-protein levels; the difference between involved and uninvolved FLC levels. The absolute increase must be $> 10 \text{ mg/dL}$ ◦ Bone marrow plasma cell percentage; the absolute percentage must be $\geq 10\%$⁵ • Definite development of new bone lesions or soft tissue plasmacytomas or definite increase in the size of existing bone lesions or soft tissue plasmacytomas • Development of hypercalcemia (corrected serum calcium $> 11.5 \text{ mg/dL}$ or 2.87 mmol/L) that can be attributed solely to the plasma cell proliferative disorder
Relapse	Clinical relapse requires one or more of: Direct indicators of increasing disease and/or end organ dysfunction (CRAB

Health Data Specialists	
DARE (EAE-2017/MM02)- Statistical Analysis Plan	Version: 1.0 EN
Author: GC, Reviewer: MS, Quality Assurance: GK	Date: 02-02-2018

	
features).⁴ It is not used in calculation of time to progression or progression-free survival but is listed here as something that can be reported optionally or for use in clinical practice
 
 • Development of new soft tissue plasmacytomas or bone lesions • Definite increase in the size of existing plasmacytomas or bone lesions. A definite increase is defined as a 50% (and at least 1 cm) increase as measured serially by the sum of the products of the cross-diameters of the measurable lesion • Hypercalcemia ($> 11.5 \text{ mg/dL}$) [2.87 mmol/L] • Decrease in hemoglobin of $\geq 2 \text{ g/dL}$ [1.24 mmol/L] • Rise in serum creatinine by 2 mg/dL or more [$177 \mu\text{mol/L}$ or more]
Relapse from CR ³ (To be used only if the end point studied is DFS) ⁶	
Any one or more of the following:
 
 • Reappearance of serum or urine M-protein by immunofixation or electrophoresis • Development of $\geq 5\%$ plasma cells in the bone marrow⁵ • Appearance of any other sign of progression (i.e., new plasmacytoma, lytic bone lesion, or hypercalcemia)

APPENDIX 2

Table 7. IMWG Renal Response Criteria

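### SAP Table 6 omits the protocol's Note for patients measurable only by free light chains, so an ORR derived from it could count an unchanged patient as VGPR

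*Protocol*

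**What the plan says.** Protocol 10.4.3 defines ORR as best response of PR or better under Appendix 4. After its table, Appendix 4 prints a Note and seven numbered footnotes. The Note is headed as "A clarification to IMWG criteria for coding CR and VGPR in patients in whom the only measurable disease is by serum FLC levels". For those patients CR also needs a normal FLC ratio, and "VGPR in such patients is defined as a" fall of more than 90% in the FLC difference (involved minus uninvolved).

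SAP 6.6.1.4 defines ORR by the SAP's own table instead ("APPENDIX 1) as their best overall response"), and DoR is restricted to patients with PR or better. Table 6 in SAP Appendix 1 carries the rows and superscripts 1 to 6, then runs straight into Appendix 2 with no Note and no footnote text. Three of its rows matter here:

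- **VGPR**, first limb: "Serum and urine M-protein detectable by immunofixation but not on electrophoresis". No change from baseline is asked for.
- **PR**, when serum and urine M-protein are not measurable: a 50% or greater "decrease in the difference between involved and uninvolved FLC levels is required in place of the M-protein criteria".
- **PD**, serum limb: a rise of at least 25% from the lowest value, under "Serum M-component and/or (the absolute increase must be" at least 0.5 g/dL.

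Two of the protocol footnotes bear on PD. Footnote 3 says "All relapse categories require two consecutive assessments made at any time before classification as relapse or disease progression". Footnote 4 says that serum rises of 1 g/dL or more "are sufficient to define relapse if starting M-component is" 5 g/dL or more.

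FLC-only patients are eligible under inclusion criterion 6 of the protocol and the matching criterion in SAP 6.1.1.

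**The concern.** The first limb of the VGPR row describes a state, not an improvement. That is harmless in a patient who had a measurable M-protein at baseline, because the state can then be reached only by responding. A patient whose disease is measurable only by serum FLC may already be immunofixation-positive and electrophoresis-negative before the first dose. The protocol Note closes this gap and the SAP table leaves it open.

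As printed, Table 6 is also out of order for such a patient, who can fail PR and still meet the higher category, VGPR.

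At stake are ORR, which could only move upward, and DoR. DoR would take in patients who had not responded. For patients who later reach a 50% fall, it would date the start of response too early.

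**Working it through.** No figure in the plan needs reproducing here. The check applies the two rule sets to the same patient.

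**1. ORR status of an FLC-only patient.** Inputs are the VGPR and PR rows of SAP Table 6, and the same rows of protocol Appendix 4 with its Note. The CR row and any plasmacytoma are set aside, and the M-protein-reduction limb of VGPR is taken as not met. IFE is immunofixation and PEP is electrophoresis.

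| IFE / PEP | Fall in FLC difference | SAP Table 6 | Protocol Appendix 4 with Note |
|---|---|---|---|
| + / − | 0% or 30% | VGPR, responder | not VGPR (needs >90%), not PR (needs ≥50%): non-responder |
| + / − | 60% | VGPR, responder | PR, responder |
| + / − | 95% | VGPR, responder | VGPR, responder |
| any other combination | 0% or 30% | non-responder | non-responder |
| any other combination | 60% or 95% | responder | responder |

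The two disagree on ORR in one cell only: IFE-positive, PEP-negative, with a fall below 50%. No footnote enters this comparison, so the missing Note alone produces the difference.

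**2. Would confirmation catch it?** No. Protocol 7.1.1 asks for a consecutive assessment, and an unchanged patient meets the same row again.

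**3. Would the data exist?** Yes. Protocol 7.1.1.1 has immunofixation done for all patients at screening and baseline, and later when M-protein disappears on electrophoresis.

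**4. Size per patient.** With about 38 enrolled, each affected patient adds 1/38 = 0.026, or 2.6 points. For scale, assume a true ORR near the 29.2% that protocol 1.2 cites for daratumumab alone: 0.292 × 38 ≈ 11 responders.

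- 11/38 = 28.9% (exact 95% CI 15.4 to 45.9)
- 12/38 = 31.6% (17.5 to 48.7)

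**5. Footnote 4 and PD.** Let N be the lowest serum value in g/dL, in a patient who started at 5 g/dL or more.

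- SAP threshold: N + max(0.25N, 0.5)
- Protocol threshold: the same, but a rise of 1.0 is enough

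They differ only when 0.25N > 1.0, that is N > 4. At N = 4 both give 5.0 g/dL. At N = 6 the SAP gives 6 + 1.5 = 7.5 g/dL and the protocol gives 6 + 1.0 = 7.0 g/dL.

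**6. Footnote 3 and PD.** Without it, the SAP's PD row carries no two-assessment rule. Protocol 7.1.1 keeps one, through laboratory confirmation of an M-protein or FLC rise and the sponsor's check of each reported progression.

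**The case against.** The strongest reply is that nothing shows response being computed from Table 6. Protocol 7.1.1 has the investigator assess response under Appendix 4, which carries the Note. The SAP's schedule has its own row for the investigator's response assessment and refers to protocol Section 7.1 for details. SAP section 1 says that the analyses follow the protocol's statistical section. Where the SAP intends programmatic assignment, as for laboratory grades, it says so. This stands, and it makes the harm conditional. It does not remove the conflict: SAP 6.6 specifies investigator assessment only for PFS, and 6.6.1.4 points ORR to a table with a different rule.

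The affected group is also narrow. M-protein that is not measurable may still be visible on electrophoresis, and such a patient does not meet the row. The row's mention of both serum and urine may narrow it further. Both points stand.

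The SAP (v1.0, 02-02-2018) predates Amendment 1 of 15 March 2018. Its age does not explain the gap. The superscripts in Table 6 have no text to point to, the Amendment 1 log refers to an existing note 4, and no amendment entry lists the FLC Note as new. Loss of text in PDF extraction cannot be fully excluded, but notes under SAP Tables 1 and 7 survived.

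ORR is a secondary endpoint reported with an exact interval, and no stopping rule depends on it. CR rate is not a listed endpoint, so the lost FLC-ratio condition for CR matters little here.

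**Conclusion.** The SAP prints a response rule that conflicts with the protocol for FLC-only patients. If ORR is derived from or checked against Table 6, every IFE-positive, PEP-negative FLC-only patient with a fall below 50% becomes a false VGPR, at 2.6 points of ORR each on 38 patients. The effect on ORR can only be upward. The documents do not give the number of such patients, so no total is offered.

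A reader might infer more, in four ways that the documents do not support:

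- **That the reported ORR will be inflated.** Scoring by the investigator under Appendix 4 would avoid this.
- **That the inflation can be sized from the 15–20% light-chain-only share in protocol 1.1.** That share describes myeloma in general. Light-chain patients may be measurable in urine, and the share who are IFE-positive and PEP-negative is not stated.
- **That the missing footnotes contribute to the false VGPR.** They do not.
- **That all patients with high M-protein progress later under the SAP, or that PD goes unconfirmed.** The delay needs a starting value of at least 5 g/dL and a lowest value above 4 g/dL, and the protocol keeps confirmation.

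**What to change.** Do one of the following in the SAP:

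- replace Table 6 with the current protocol Appendix 4, including the FLC-only Note and footnotes 1 to 7; or
- delete Table 6 and define ORR, DoR and PD by protocol Appendix 4.

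In either case, add to SAP 6.6.1.4 that ORR uses the investigator's Appendix 4 response category, and that for FLC-only patients the immunofixation/electrophoresis limb of VGPR does not apply.

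The cost is one SAP wording amendment and no new data. ORR may come out slightly less favourable than one derived from Table 6 as printed.
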